### 8.3.2 Efficacy Analyses

The primary efficacy endpoint will be analyzed using a repeated measures analysis of covariance on change-from-baseline variable to compare the time profile between treatments where the visit will be the time factor; and the stratification factors, treatment group, and interaction term for treatment-by-visit will be the fixed effects and the baseline value will be the covariate. An unstructured variance-covariance matrix will be used. Additional interaction terms will also be included in supportive statistical models and will be detailed in the SAP.

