3.5 Changes to the Analysis from the Protocol

Section 8.3.2 of the protocol mentions the inclusion of stratification factors as fixed effects in the statistical model. The biopsy collection stratification factor was included for an operational purpose only (to have samples for biopsy in the four treatment groups), therefore this variable was not included in any of the statistical models. In addition, for the primary endpoint EASI, the baseline value will not be included as covariate in the statistical model, since it is already included as stratification factor (baseline disease severity) and to include both variables would create a problem of multicollinearity.

In section 8.3.2 of the protocol, Bonferroni adjustment was proposed to adjust for the multiple dose comparisons between ASN002 and placebo. It is well known that the Bonferroni adjustment is overly conservative. Therefore, Hochberg adjustment will be used for the multiple dose comparisons. The decision for this change was made before the unblinding. Since this change would not affect the conduct of the trial in any sense, no protocol amendment was made to account for this change.

The section 8.3.3 of the protocol has planned for summary of physical exams using descriptive statistics presenting the value at each visit as well as the change from baseline. Since significantly

	STATISTICAL ANALYSIS PLAN, Version Final 2.0
Protocol Number: ASN002AD-201 V3.0	Sponsor: Asana BioSciences, LLC

abnormal physical exams will be presented in the summary of AEs, only listings of physical exams will be presented.

The following endpoints are listed in the protocol:

- 1) Proportion of subjects achieving at least a 2-grade reduction from baseline to clear (0) or almost clear (1) in Investigator's Global Assessment (IGA) at Weeks 2, 4, 8, and 12
- 2) Proportion of subjects achieving an IGA of clear (0) or almost clear (1) at Weeks 2, 4, 8, and 12

Since the study has an inclusion criterion of 3 and 4 on IGA, both endpoints will contain exactly the same set of subjects. For this reason, only the first endpoint listed above will be provided.

Data from site 027 has been deemed unreliable. For this reason, all data from this site will be excluded from all analysis for this study (both safety and efficacy).

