5.1 Sample Size

Using the following assumptions for the primary efficacy endpoint: a change-from-baseline in EASI at week 12 of at least -15 in the ASN002 dosing groups, a change-from-baseline of -8 in the placebo group, a common standard-deviation of 8, nominal alpha of 0.0167 for each comparison of interest, we would need 40 evaluable subjects per group in order to achieve a power of 92% on the primary efficacy endpoint.

Moreover, with 46 subjects per group, we would have 80% power to show a statistically significant difference between the higher dosing group and placebo in IGA responses (one of the key secondary efficacy endpoint), assuming a response of 37.5% vs. 11.1% in the higher dosing and placebo groups, respectively, using an alpha of 5%.

Thus, assuming about 15% dropout rate, 55 subjects per group will need to be enrolled in this trial for a total of 220 subjects in order to have a minimum of 46 subjects per group to evaluate efficacy with adequate power.

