6 STATISTICAL CONSIDERATIONS

6.1 Adjustments for Covariates

Baseline value for the absolute change from baseline of continuous efficacy parameters will be included as covariate in the statistical models.

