1. If one question is left unanswered this is scored 0 and the scores are summed and expressed as usual out of a maximum of 30.
2. If two or more questions are left unanswered the questionnaire is not scored.
3. If question 7 is answered 'yes' this is scored 3 even if in the same question one of the other boxes is ticked.
4. If question 7 is answered 'no' or 'not relevant' but then either 'a lot' or 'a little' is ticked this is then scored 2 or 1. If it is answered 'no', but the second half is left incomplete, the score will remain 0.

DLQI will be assessed as

- the change from baseline in DLQI at Weeks 2, 4, 8, and 12.

Secondary Endpoint Analyses

The same methods (MMRM and ANOVA) as described for the primary efficacy analyses (Section 12.1) will be performed to analyze the change and percent change in EASI.

Similar methods (MMRM and ANCOVA) as described for the primary efficacy analyses (Section 12.1) will be performed to analyze the change and percent change in NRS, SCORAD (MMRM and ANCOVA for total score; MMRM only for sleep and pruritus sub-scores) and BSA, and the change in 5D-Pruritus Scale (change from baseline only), POEM (change from baseline only) and DLQI (change from baseline only), with the addition of the baseline score as covariate in the models. Analyses will be based on the mITT population for all secondary parameters.

For categorical efficacy endpoints involving proportions of IGA, EASI and NRS (e.g. the proportion of subjects achieving at least a 2-grade reduction from baseline to clear (0) or almost clear (1) in Investigator's Global Assessment (IGA) at week 12), a Cochran Mantel Hansel test (CMH) controlling for the stratification variable (baseline disease severity) will be performed. For subgroup analyses at each level of baseline severity, a Chi-squared test will be performed. Analyses will be based on the mITT population for all secondary parameters and also on PP population for IGA.

	STATISTICAL ANALYSIS PLAN, Version Final 2.0
Protocol Number: ASN002AD-201 V3.0	Sponsor: Asana BioSciences, LLC

As a sensitivity analysis for IGA, the Cochran Mantel Hansel test (CMH) controlling for the stratification variable (baseline disease severity) will be performed, excluding the subjects for whom the IGA form was initially used to capture the vIGA assessment at baseline. This sensitivity analysis will be performed on the mITT and PP populations.

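### The SAP drops continuous baseline EASI from the primary model on a multicollinearity ground that does not hold, no sensitivity analysis restores it, and SAP 6.1 still says the opposite

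*SAP*

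**What the plan says.** In Protocol 8.3.2 the primary repeated-measures model has treatment, visit, their interaction and the stratification factors, and "the baseline value will be the covariate". The Week 12 ANCOVA listed there as a sensitivity analysis is adjusted in the same way.

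SAP 3.5 declares two departures. The biopsy stratum is left out as purely operational. Separately, "for the primary endpoint EASI, the baseline value will not be included as covariate in the statistical model"; the reason given is that the severity stratum already represents baseline and "to include both variables would create a problem of multicollinearity". SAP 12.1 carries this out. The MMRM has treatment, visit, the three-level severity stratum and treatment-by-visit, and the Week 12 model becomes an ANOVA on treatment and stratum.

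Two other SAP sections bear on this:

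- SAP 6.1, without an exception for EASI: "Baseline value for the absolute change from baseline of continuous efficacy parameters will be included as covariate in the statistical models".
- SAP 12.2, for EASI change and percent change: "The same methods (MMRM and ANOVA) as described for the primary efficacy analyses (Section 12.1) will be performed", so without baseline. For NRS, SCORAD, BSA, 5-D, POEM and DLQI it uses similar models "with the addition of the baseline score as covariate in the models".

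**The concern.** The treatment contrast is the quantity of interest, and collinearity between two adjustment terms is not a reason to drop one of them unless it harms that contrast. The stratum is also a poor stand-in for the score: its top level runs from 30 to the scale maximum of 72 (Protocol 7.1.1).

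If change depends on baseline within strata, leaving the score out does two things. The standard error is larger than it need be, and chance baseline differences between arms within a stratum go uncorrected. Some dependence is plausible, because EASI cannot fall below zero and so baseline limits the possible improvement.

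The sensitivity and supportive analyses in SAP 12.1 are the ANOVA, pooled site, exclusion of site 029, a nonparametric analysis, IWRS strata, and EASI data after prohibited medication. None contains baseline EASI, so the effect of this departure from the protocol on the primary result would not be visible.

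**Working it through.** **1. The plan's own figure.** SAP 5.1 gives mean changes of -15 and -8 (difference 7), "a common standard-deviation of 8", alpha 0.0167 and 40 evaluable per group. SE = 8 × √(2/40) = 1.789, noncentrality 7/1.789 = 3.91, 78 df. Two-sided power is 92.6%, which reproduces the stated 92%. At 46 per group it is 95.9%.

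**2. Assumptions.** The documents give no baseline EASI distribution and no baseline-change correlation. I took baseline as 16 plus an exponential (mean 8, 12.8 or 16, cut at 72) or a truncated normal (28, 12), and held the raw SD of Week 12 change at 8. Below, r is the absolute baseline-change correlation and R² is the share of baseline variance lying between strata (cuts at 21.25 and 29.95).

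| Baseline | SD | R² | Share of within-stratum variance in the ≥30 stratum |
|---|---|---|---|
| 16 + exp(8) | 7.8 | 0.79 | 75% |
| 16 + exp(12.8) | 11.1 | 0.73 | 92% |
| 16 + exp(16) | 12.5 | 0.71 | 94% |
| Truncated normal | 9.5 | 0.70 | 91% |

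The strata leave 21-30% of baseline variance unexplained, most of it in the open top stratum.

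**3. Cost of collinearity to the contrast.** Over simulated stratified allocations with residual SD held fixed, adding the score multiplies the variance of the dose-placebo contrast by 1.005 on average at 55 per arm (95th percentile about 1.02) and by about 1.007 at 40 per arm (95th percentile about 1.025). This is so even though the score's own variance inflation factor given the strata, 1/(1 - R²), is about 3.3 to 4.8.

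**4. Gain from the score, single timepoint.** Residual variance is 64(1 - r²R²) with strata only and 64(1 - r²) with strata plus score, so the ratio is (1 - r²R²)/(1 - r²):

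| r | Ratio over the four distributions |
|---|---|
| 0.2 | 1.009-1.012 |
| 0.4 | 1.039-1.056 |
| 0.6 | 1.116-1.166 |
| 0.7 | 1.20-1.28 |

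At r = 0.4 and 40 per arm the SE is 1.67-1.69 without the score and 8 × √0.84 × √(2/40) = 1.64 with it.

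Break-even against the 0.5% cost is at r² = 0.005/(1 - R² + 0.005). That is r of about 0.13-0.15, or an absolute slope (8r divided by the baseline SD) of about 0.08-0.16.

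**5. Gain in the MMRM itself.** Simulated with 3000 trials per setting, 55 per arm, four visits, unstructured covariance and 15% monotone dropout. The table gives the empirical variance of the Week 12 contrast under the SAP model relative to the model with baseline:

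| r | Common baseline slope | Baseline-by-visit |
|---|---|---|
| 0 | 0.995-1.000 | 0.994-0.998 |
| 0.2 | 1.004-1.008 | 1.007-1.010 |
| 0.4 | 1.027-1.041 | 1.032-1.052 |
| 0.6 | 1.089-1.146 | 1.110-1.179 |

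Absolute bias was at most 0.054 EASI points in every model, which is simulation noise.

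**6. Chance imbalance.** At 55 per arm the stratum-adjusted baseline difference between two arms has SD = baseline SD × √(1 - R²) × √(2/55), or 0.7-1.3 EASI points. At r = 0.4 (absolute slope 0.26-0.41) this is an uncorrected shift with SD of about 0.3 points.

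**7. Power if the effect is smaller than planned.** For an assumed 5-point difference at 46 per arm, the single-timepoint ratios give 77.0-77.7% without and 79.5% with the score at r = 0.4, and about 85-86% against 90% at r = 0.6. The common-slope MMRM ratios narrow this slightly: 77.7-78.3% against 79.5%, and 85.3-87.3% against 90.2%.

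**8. A plausible range for r.** As an illustration only, suppose improvement is proportional to baseline and the planned means hold. The four-arm mean improvement is (3 × 15 + 8)/4 = 13.25. Divided by assumed mean baselines of about 24 to 31.5, this is a slope of 0.55 to 0.42, with r about 0.50-0.68. The true slope could be smaller.

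**The case against.** Baseline EASI is not ignored. The MMRM keeps it as a three-level factor, randomisation is stratified on it, and the strata carry 70-79% of its variance under the assumptions above. The change is disclosed in the section meant for such changes, in a SAP written before database lock and final unblinding. At the planned 7 points, 46 per arm and r = 0.4, power is 97.7-97.9% without the score and 98.3% with it. The larger losses need r of 0.6 or more, and the 5-point effect is not a planning value. All of this stands, and it limits the consequence to precision.

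The comparison with SAP 12.2 is only partly telling. The severity stratum is a cut of EASI itself, not of SCORAD or BSA, so the redundancy argument is specific to EASI. But redundancy is a matter of degree, and steps 2 and 3 show that the score keeps information at almost no cost.

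Baseline EASI is also summarised, effects by severity stratum are reported, and percent change is analysed. These give some view of the role of baseline, but none is a baseline-adjusted estimate of the primary contrast.

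Finally, SAP 6.1 is a general sentence and the specific sections agree with one another, so the intended model is clear. SAP 6.1 is simply the section left unreconciled.

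**Conclusion.** The concern holds, and the point should be fixed. The multicollinearity rationale is not valid for a randomised contrast, and the protocol's covariate was removed from the primary model with no planned analysis to show the effect. There is no bias and no type I error inflation, and the planned power is safe if 8 is the raw SD of change.

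The loss depends on a correlation that the documents do not give. Adding the score gains nothing below r of about 0.13-0.15. In the MMRM with a common baseline slope, the SAP model's excess variance is below 1% at r = 0.2, about 3-4% at r = 0.4 and 9-15% at r = 0.6. Excess of 20% or more needs r near 0.7 (single-timepoint formula). These ranges rest on the assumed baseline distributions and a raw SD held at 8.

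**What to change.** In SAP 3.5 and 12.1, put continuous baseline EASI back alongside the severity stratum in the primary MMRM and in the Week 12 absolute-change model (ANCOVA in place of ANOVA), and delete the multicollinearity rationale. A baseline-by-visit term is preferable, though it goes beyond the protocol's model. This brings SAP 12.1 into line with SAP 6.1 and with the protocol's baseline covariate. The disclosed omission of the biopsy stratum remains a separate difference from the protocol.

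At minimum, name the baseline-adjusted MMRM as a sensitivity analysis, correct the rationale in SAP 3.5, and write the EASI exception into SAP 6.1.

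The cost is SAP wording and about one degree of freedom (a few more with baseline-by-visit). No new data are needed.

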4 POPULATIONS FOR ANALYSIS

4.1 Modified Intent-to-Treat Population

The modified intent-to-treat (mITT) population will include all randomized subjects who received at least one dose of the study product. All subjects will be analyzed according to the treatment group to which they were randomized. The mITT population will be used as the primary analysis population for efficacy.

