4.3 Safety Population

The safety population will include all subjects who received at least one dose of the study product. All subjects will be analyzed according to the treatment that they actually received.

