6.2 Handling of Dropouts or Missing data

See Appendix 2 for handling of completely or partially missing dates for prior and concomitant medications and adverse events.

For safety analyses, no imputation of the data will be done and analyses will be conducted on the observed cases (OC). All efficacy analyses will be performed using Mixed Model Repeated Measures (MMRM) analyses as primary analyses to take care of missing observations. (See section 12.1).

For subjects starting prohibited medications as listed in section 6.4.2 of the protocol, all efficacy data captured after the start of prohibited medication will be considered missing for the analysis

	STATISTICAL ANALYSIS PLAN, Version Final 2.0
Protocol Number: ASN002AD-201 V3.0	Sponsor: Asana BioSciences, LLC

of those parameters. A sensitivity analysis on the primary endpoint EASI will be done including all efficacy EASI data for these subjects (before and after the prohibited medication).

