6.4 Multicenter Studies

To obtain a sufficient and better-balanced number of subjects among study sites, pooling of sites within each country will be applied. Sites without at least 10 subjects in the mITT population will be incorporated into pooled sites as described below. German sites will be pooled together, USA sites will be pooled together and Canadian sites will be pooled together.

Sites in USA or Canada (for each country separately):

- 1) Sites with less than 10 subjects in the mITT will be pooled within a country:
 - a. Sites with less than 10 subjects will be ordered from lowest to highest in terms of number of mITT subjects. In case of ties, the ordering for tied sites will be determined according to the site identification number (from smallest to largest).
 - b. Sites will be combined beginning at the smallest until the resulting pooled site contains at least 10 mITT subjects. The sites pooled in this way will be considered as a single site in the statistical analyses.
 - c. The process described above will resume for the remaining sites not meeting the criterion of at least 10 mITT subjects. If the final set of pooled sites does not meet the criterion of at least 10 mITT subjects, the final set will be pooled with the preceding pooled site.
 - d. If there is only one site with less than 10 mITT subjects, then this site will be combined with the site with the second lowest number of subjects. As above, in the

	STATISTICAL ANALYSIS PLAN, Version Final 2.0
Protocol Number: ASN002AD-201 V3.0	Sponsor: Asana BioSciences, LLC

case of ties, the ordering for tied sites will be determined according to the site identification number (from smallest to largest).

In the case where less than 10 mITT subjects are available in one country, the subjects from both countries will be pooled.

Sites in Germany

- 1) Sites with less than 10 subjects will be ordered from lowest to highest in terms of number of mITT subjects. In case of ties, the ordering for tied sites will be determined according to the site identification number (from smallest to largest).
- 2) Sites will be combined beginning at the smallest until the resulting pooled site contains at least 10 mITT subjects. The sites pooled in this way will be considered as a single site in the statistical analyses.

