Information for stratification factor will be taken from the Electronic Data Capture (EDC) database, and not the IWRS for primary analysis.

Sensitivity Analyses

An analysis of variance (ANOVA) will be performed, where the absolute change from baseline in EASI score at Week 12 will be the dependent variable, the treatment group and stratification factor (baseline disease severity) will be fixed effects. A supportive analysis with pooled site and pooled

	STATISTICAL ANALYSIS PLAN, Version Final 2.0
Protocol Number: ASN002AD-201 V3.0	Sponsor: Asana BioSciences, LLC

site-by-treatment interaction included as fixed factors in addition to the other factors listed above will be performed in order to study the impact of pooled site on efficacy. If the pooled site-by-treatment interaction is not statistically significant, it will be removed from the model.

An additional sensitivity analysis will be carried out on the change from baseline in EASI score at Week 12 where data from site 029 is excluded.

Distribution of residuals will be visually examined to determine whether substantial departures from normality and homogeneity of variance are apparent. If the data are inconsistent with the assumption of normality, a nonparametric analysis of variance will be performed.

Additional sensitivity analyses will be performed using the stratification factor as per IWRS database in the primary efficacy MMRM model described above and including all efficacy EASI data for these subjects (before and after the prohibited medication).

	STATISTICAL ANALYSIS PLAN, Version Final 2.0
Protocol Number: ASN002AD-201 V3.0	Sponsor: Asana BioSciences, LLC

Subgroup Analyses

An analysis of variance (ANOVA) will be performed, where the absolute change from baseline or the percent change from baseline in EASI score at Week 12 will be the dependent variable, the treatment group and stratification factor as per EDC (baseline disease severity, [EASI = 16.0-21.2] vs. [EASI = 21.3-29.9] vs. [EASI = \geq 30.0] and treatment-by-stratification factor will be fixed effects. Treatment effect per stratification factor subgroup will be presented as well as associated p-values.

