13 SAFETY ANALYSIS

All safety analyses will be conducted using the safety population.

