16 APPENDICES

Appendix 1

Output Conventions

TLF will be generated using SAS® and will be displayed on letter size paper with landscape orientation, 1 inch margins and 9 pt Courier New font.

The header section will comprise the sponsor's name, the protocol number, the delivery description, the data cut-off date (if applicable), the TLF number, the TLF title, the population, and the page number (Page X of Y). The footer section will include the TLF footnotes, the CRO's name, the date and time of the execution of the program, and the name of the program.

P-values ≥ 0.0001 will be reported to 4 decimal places; p-values less than 0.0001 will be reported as “<0.0001”; p-values greater than 0.9999 will be reported as “>0.9999”.

Mean, median, and quantiles will be displayed to one more decimal place than the original value; minimum and maximum will keep the same number of decimal places as the original value; standard deviation, standard error, and CI will be displayed to two more decimal places than the original value. If derived parameters are to be summarized, the number of decimals of the derived values is to be chosen on a case-by-case basis, but the rule above applies.

For categorical summary tables, percentages will be reported to one decimal place. Percentages between 0 and 0.1 (both exclusive) will be displayed as “<0.1”. The denominator for each percentage will be the number of subjects within the population per treatment group unless otherwise specified.

Listings will be ordered by treatment group, subject number, date, and visit (where applicable). Imputed dates and imputed missing data will not be presented in the listings.

Dates & Times Format

Date and time (if available) will be presented in the format yyyy-mm-dd/hh:mm.

	STATISTICAL ANALYSIS PLAN, Version Final 2.0
Protocol Number: ASN002AD-201 V3.0	Sponsor: Asana BioSciences, LLC

Presentation of Treatment Groups

When applicable, study treatments will be represented as follows in the different outputs:

Study Treatment Full Names	Study Treatment Output Names
ASN002 40 mg	ASN002 40mg
ANS002 60 mg	ASN002 60mg
ASN002 80 mg	ASN002 80mg
Placebo	Placebo

	STATISTICAL ANALYSIS PLAN, Version Final 2.0
Protocol Number: ASN002AD-201 V3.0	Sponsor: Asana BioSciences, LLC

Appendix 2

Algorithm for Imputation of Start/End Date of Adverse Events and Prior/Concomitant Medications

Event Start Date Imputation

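### Site 027 is removed from every safety and efficacy analysis, but the analysis sets are not amended, its dosed subjects' serious events have no assigned place in the reported results, and the primary result is never shown with the site included

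*SAP*

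**What the plan says.** SAP 3.5, which lists departures from the protocol, calls the data of site 027 unreliable and rules that "all data from this site will be excluded from all analysis for this study (both safety and efficacy". It gives no criterion, date, number of subjects or split by arm. The site is not mentioned anywhere else in the SAP.

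The sections that this rule has to change read as follows:

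- SAP 4.1: the mITT population "will include all randomized subjects who received at least one dose of the study product".
- SAP 4.3: "The safety population will include all subjects who received at least one dose of the study product".
- SAP 13: "All safety analyses will be conducted using the safety population".
- SAP Appendix 1: "The denominator for each percentage will be the number of subjects within the population per treatment group unless otherwise specified".
- SAP 6.4, on pooling of sites: "Sites without at least 10 subjects in the mITT population will be incorporated into pooled sites as described below".

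SAP 13.1 also plans listings of all AEs, of fatal AEs and of serious AEs, without saying whether site 027 is in them.

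For the primary endpoint, one sensitivity analysis concerns a single site. It is run "on the change from baseline in EASI score at Week 12 where data from site 029 is excluded", which is a different site. For subjects who start prohibited medication, SAP 6.2 plans a run that restores the removed data: "A sensitivity analysis on the primary endpoint EASI will be done including all efficacy EASI data for these subjects".

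**The concern.** Keeping unreliable data out of the pooled estimates can be justified. Leaving the serious events and exposure of dosed subjects with no assigned place in the results is a different matter. These people took study product, and a death or SAE among them is part of the safety record of the arm to which they were randomized, even if the site's scoring or record-keeping cannot be trusted. The SAP plans no separate output that would show such events.

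On efficacy, dropping a whole site is a larger step than the one examined for site 029, yet only site 029 gets a with-and-without comparison. A reader of the results could not see what removing site 027 did to the primary estimate. The safety part carries the weight; the efficacy part is secondary.

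**Working it through.** **1. Do the sections agree?** SAP 3.5 excludes data, while SAP 4.1 and 4.3 define sets of subjects by receipt of a dose. Neither set has a site exception, and SAP 13, Appendix 1 and 6.4 all build on those sets. The rule is therefore stated once and not carried into the definitions that it alters.

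**2. Is there another route by which the data are reported?**

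| Planned output | Shows site 027? |
|---|---|
| Safety summaries (SAP 13) | No, under SAP 3.5 |
| Listings of all AEs, deaths and SAEs (SAP 13.1) | Not stated |
| Disposition and population listings (SAP 7.1) | Probably: all consented subjects are accounted for, and Protocol 6.3 puts the site number in the subject identifier |
| Primary MMRM, on mITT and PP (SAP 12.1) | No |
| Sensitivity runs (SAP 6.2, 12.1): ANOVA, pooled site, site 029 removed, nonparametric if needed, IWRS strata, data after prohibited medication | None restores the site |

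**3. The plan's own figures (SAP 5.1).** Difference 15 − 8 = 7, SD 8, two-sided alpha 0.0167, 40 per group. The two-sample t calculation gives 92.6% power, against 92% stated. With 55 per group and 15% dropout, 55 × 0.85 = 46.75 are evaluable. The plan's figure reproduces.

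**4. Assumed site size.** The documents give none. The planned average is 220/50 = 4.4 subjects per site. I take 4 to 20 of 220 (1.8% to 9.1%), spread evenly, so 1 to 5 of 55 per arm. The upper end and the even spread are assumptions; randomization is not stratified by site.

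**5. Safety.** One omitted subject with an SAE is 1/55 = 1.8 percentage points of an arm. If 2 of the 220 subjects had a given rare event, and site 027 were no different from the rest in this respect, the chance that at least one of them is at the site would be:

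- 4 subjects: 1 − (216 × 215)/(220 × 219) = 3.6%
- 20 subjects: 1 − (200 × 199)/(220 × 219) = 17.4%

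**6. Efficacy, 20 site subjects with no effect at the site.**

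- SE with the site: 8 × √(2/46.75) = 1.655. Without it, n = 50 × 0.85 = 42.5 and SE = 8 × √(2/42.5) = 1.735. The other sites make up 200/220 = 0.909 of the total.
- At the planned effect: with the site, 7 × 0.909 = 6.36 and 6.36/1.655 = 3.85. Without it, 7/1.735 = 4.03. The conclusion is the same.
- p = 0.05 with the site: the estimate is 1.96 × 1.655 = 3.24, so the rest is 3.24/0.909 = 3.57. Without the site, 3.57/1.735 = 2.06, p about 0.040.
- p = 0.05 without the site: the estimate is 1.96 × 1.735 = 3.40. With the site, 3.40 × 0.909 = 3.09 and 3.09/1.655 = 1.87, p about 0.062.

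**7. Power for the primary endpoint after exclusion.** 45.9 evaluable per arm (4 site subjects) gives 95.8%, and 42.5 (20 site subjects) gives 94.2%. Both exceed the stated 92%. The plan's 46 per group for IGA would be narrowly to modestly missed, but any exclusion of subjects would do that, and it is not the point here.

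**The case against.** The strongest reply is that SAP 3.5 is the proper place for a departure and overrides the later sections. Dosing records are site data too, so the natural reading is that site 027 subjects leave the mITT and safety sets altogether, and numerators, denominators and pooling counts then agree. I accept that reading. On it, failing to repeat the rule in SAP 4.1 and 4.3 is a matter of wording. But it confirms the omission: the subjects leave the safety summaries and nothing takes their place.

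It is also fair that site 029 and site 027 are not mirror images. Site 029 stays in the primary analysis, so testing its removal is natural; restoring data already judged unreliable may tell the reader little. That makes the extra MMRM secondary. It does not answer the safety point.

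Safety oversight during the trial is not in question: expedited SAE reporting (Protocol 7.6.7) and DSMB review of unblinded data (Protocol 4.5) are unaffected. Neither puts these events into the reported results.

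A reader might infer more than the documents support:

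- *That the exclusion was driven by results.* SAP 1 places the SAP before database lock and final unblinding. SAP 3.5 says explicitly that the Hochberg change preceded unblinding and has no such sentence for site 027, but that silence is not evidence of an unblinded decision.
- *That AE rates are diluted because site 027 subjects stay in the denominator without data.* The wording does not rule this out, but it is the less natural reading and nothing here rests on it.
- *That a borderline result could swing widely.* At the planned 7-point effect the estimate moves by 0.64 points, but that shift cannot be carried over to a result near p = 0.05, where the whole estimate is only about 3.2 points.
- *That disposition loses the subjects.* SAP 7.1 already accounts for everyone who consented.

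**Conclusion.** The concern holds as a gap in reporting, not as a bias or power problem. SAP 3.5 takes all site 027 data out of safety and efficacy analysis, SAP 4.1, 4.3 and 13 are not amended to match, the safety summaries omit the site's dosed subjects, the coverage of the 13.1 listings is unclear, and the primary endpoint is never shown with the site in.

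The size is conditional. It presumes that the site dosed at least one subject, which the reference to its data implies but no count confirms. The safety figure of 1.8 percentage points per affected subject holds for a 55-subject arm; how many subjects are affected is unknown. On efficacy, even at an assumed 20 site subjects with no effect at the site, p moves only between 0.05 and about 0.040 or 0.062. That could matter for a dose comparison close to its Hochberg threshold and not otherwise. The conclusion at the planned effect does not change, and the stated 92% power is not at risk.

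**What to change.** Keep the exclusion from the primary efficacy analysis and from the pooled safety tables. Then:

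1. Add a separate flagged table and listing for site 027: randomized and dosed counts by arm, exposure, deaths, SAEs and discontinuations due to AEs. State that the SAP 13.1 listings include these subjects.
2. State in SAP 4.1 and 4.3 that site 027 subjects leave the analysis sets, so that numerators, the Appendix 1 denominators and the SAP 6.4 pooling counts refer to the same people.
3. As a secondary item, add one sensitivity run of the primary MMRM with site 027 included, labelled as using data of doubtful reliability.

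This is a cheap improvement: SAP wording, one table and listing, and one more model run beside the site-level run already planned for site 029. No new data collection is needed. The downside is output with a data-quality caveat; if the site's records are broadly unreliable, the added MMRM in particular may be hard to interpret.
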